Erenumab will be stored refrigerated at 2°C to 8°C (36°F to 46°F) until time of use. Once removed from the refrigerator, it will be kept at room temperature and used within 7 days. Prior to administration, erenumab will sit at room temperature for at least 30 minutes, protected from direct sunlight.

Daily Headache Diary

A daily headache diary will be completed for the next 4 weeks to allow for assessment of changes in headache frequency and intensity. Headache diary data will be analyzed to classify patients as “responders” (50% or greater reduction in headache frequency at week 4 post erenumab treatment compared to frequency during the screening phase) or “non-responders” (less than 50% reduction in headache frequency at week 4 post erenumab treatment compared to the frequency during the screening phase). Since patient outcomes will be measured at 4 weeks (opposed to 12 weeks like it is done in the majority of clinical trials), depending upon patient outcomes other definitions of “response” and “non-response” could be used.

Acute Headache Therapy: Patients will be allowed to use acute headache treatments including NSAIDs during the study if needed. The use of these treatments will be recorded.

Table: Schedule of Events

	Screening Phase (7 days) (Day -7)	Baseline Visit (Day 0)	Weekly, weeks 1-4 (Day 0 to Day 28)	Follow-up Visit, week 4 (Day 28)	Safety follow-up visit, week 8 (Day 56)
Visit Window (days)	-2	+/- 0	n/a	+/- 3	+/- 3
Eligibility: I/E criteria	X				
Vital signs	X	X		X	X
Demographics, PMH	X				
Urine pregnancy test	X	X			
Headache characteristics	X			X	X
Concomitant medications / treatments	X			X	X
BDI		X		X	
STAI		X		X	
MIDAS		X		X	
PGIC				X	
Adverse events			X	X	X
Headache diary, daily	X		X		
Treatment: Erenumab injection		X			

Sample Size

A sample size of 20 will have 80% power to detect a decrease of frequency of headache days (in 28-day period) of 2 or more from baseline, assuming a standard deviation of 3, using a paired t-test with a 0.05

two-sided significance level. It is anticipated that up to 25 patients will be enrolled in the study in order to obtain 20 evaluable patients for the primary outcome.

Subject Recruitment and Screening

Subjects will be recruited from the Mayo Clinic Arizona Headache and Neurology clinics, from the clinical practices of colleagues practicing in the Phoenix region, and via posting of IRB-approved recruitment materials.

Subject Compensation

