This is a prospective, open-label, study of patients with hemicrania continua treated with a single dose of erenumab 140 mg SQ. Estimates of efficacy (decrease in frequency of headache) will be assessed. For the primary endpoint, patients will be classified as a responder (50% or greater reduction by week 4 post erenumab treatment) or a non-responder (less than 50% reduction in headache frequency). SAS version 9.4 (SAS Institute, Cary, NC) will be used for analysis. The analysis will be kept descriptive and efficacy will be evaluated based on clinical meaningfulness threshold.

Analysis Plans

Primary endpoint & analyses: All eligible patients that successfully complete the screening phase and have initiated treatment with erenumab will be considered evaluable for assessing the primary endpoint. The primary endpoint of this trial will consist of the proportion of patients who are considered to have a response as defined above at the end of week 4 divided by the total number of evaluable patients on the study. Patients will not be considered evaluable if they did not complete the screening phase requirements or discontinued the study due to withdrawal before receiving erenumab. A point estimate and two-sided 95% confidence interval will be computed for this endpoint based on properties of the binomial distribution.

The analysis plan for additional (secondary) endpoints are listed below.

Headache days (>4 hours moderate/severe pain) weeks 4 compared to baseline: Change in headache days at the end of weeks 4 will be compared to baseline. Headache frequency will be described at each time point using the mean, 95% confidence interval, median, and range. Changes from baseline in headache frequency will also be described using the mean, 95% confidence interval, median and range, and assessed using paired t-tests or non-parametric Wilcoxon signed-rank tests as appropriate. Graphical procedures will include plots of average headache frequency over time. The proportion of responders will be computed at week 4. Response at the end of week 4 is the primary endpoint.

Headache hours (moderate/severe pain intensity): Change in the amount of total headache hours (with moderate or severe pain) at the end of week 4 will be compared as separate time points to baseline. Headache hours will be analyzed similar to specific aim #1 as above.

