Acute medication use (# days over weeks 4): Acute medication use at the end of week 4 will be compared as separate time points to baseline. Medication usage will be analyzed similar to specific aim #1 as above.

Remission rate (proportion of patients free of headache weeks 4): The proportion of patients who do not have any occurrence of headache at the end of week 4 will be divided by the total number of evaluable patients in the study. A point estimate and confidence interval will be computed for these endpoints, headache freedom at week 4.

Patient-reported Outcomes: Patients will complete the BDI, STAI, MIDAS, 4-week Follow-up Headache Characteristics and the PGIC. Patient reported outcomes (BDI, STAI, MIDAS) will be scored using published scoring algorithms and described at each time point using the mean, 95% confidence interval, median, and range. Changes from baseline will also be described using the mean, 95% confidence interval, median and range, and assessed using paired t-tests or Wilcoxon signed-rank tests as appropriate. Graphical procedures will include plots of average values over time. The PGIC will be described to assess patient perception of improvement.

Adverse Events Analysis: The proportion of subjects experiencing adverse events, the nature of the adverse events, as well as severity and relationship of the adverse events to the study will be reported using descriptive statistics. The proportion of subjects with adverse events that led to withdrawal from the study will also be reported. All subjects who received at least one dose of erenumab will be included in the safety analysis. The maximum grade for each type of adverse event will be summarized as the number of patients experiencing the event divided by the total number of evaluable patients. Frequency tables will be constructed. Additionally, the relationship of the adverse event(s) to the study treatment will be taken into consideration.

Results Reporting on ClinicalTrials.gov: At study activation, this study will have been registered within the “ClinicalTrials.gov” website. The Primary and Secondary Endpoints (ie, “Outcome Measures”) along with other required information for this study will be reported on ClinicalTrials.gov.

Protocol Approval and Maintenance by IRB

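### The plan lets the definition of response depend on patient outcomes and does not confine other definitions to supportive use

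*Combined protocol and SAP*

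**What the plan says.** The Daily Headache Diary section classes a patient as a responder on a "50% or greater reduction in headache frequency at week 4 post erenumab treatment compared to frequency during the screening phase". The next sentence gives a reason, "Since patient outcomes will be measured at 4 weeks (opposed to 12 weeks like it is done in the majority of clinical trials", and then a permission: "depending upon patient outcomes other definitions of “response” and “non-response” could be used". It names no alternatives, no time or rule for choosing one, and no limit on how one may be used.

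The Statistical Methods & Analysis section states the rule without conditions: "For the primary endpoint, patients will be classified as a responder (50% or greater reduction by week 4 post erenumab treatment". Under Analysis Plans, the primary endpoint is the "proportion of patients who are considered to have a response as defined above at the end of week 4", divided by the number of evaluable patients, and "A point estimate and two-sided 95% confidence interval will be computed for this endpoint based on properties of the binomial distribution". The analysis is described as descriptive. Efficacy is to be judged against a clinical threshold for which no number is given. Neither section mentions the permission in the diary section.

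**The concern.** The clause concerns the same responder classification that forms the primary endpoint, and what triggers it is the observed outcomes. It can be read in two ways. It may allow extra descriptions alongside a fixed 50% primary result, or it may allow a replacement primary definition chosen once results are visible. The plan does not say which.

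The stated reason does not support the permission. Measurement at 4 rather than 12 weeks is a design feature known before the first patient enrols. It could justify choosing a different definition now, but not letting the results decide.

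The design makes this matter more. The study is open-label with one group, and nothing keeps diary results from the team before a definition is settled. With no control group, the reported proportion carries the conclusion by itself. If the most favourable definition became primary, that proportion would be biased upward and the interval's errors would move to the favourable side.

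**Working it through.** **The plan's own figure.** The Sample Size section claims 80% power with 20 patients "to detect a decrease of frequency of headache days (in 28-day period) of 2 or more from baseline", with SD 3 and a two-sided 5% paired t-test. With 19 degrees of freedom and noncentrality (2/3)·√20 = 2.98, exact power is 80.7%, so the figure reproduces. It concerns mean change and does not depend on how response is defined.

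**Inputs for the illustrations.** From the documents: n = 20, a decrease of 2 days per 28, the 50% cut and a 95% binomial interval (exact Clopper-Pearson used here). Everything else is an assumption, because the plan lists no alternative definitions and assumes no response rate.

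**Illustration 1: reporting the best of several non-nested definitions.** An example would be headache hours instead of headache days. Each definition is given the same true rate.

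- At a true rate of 30%, the lower limit exceeds 30% when at least 11 of 20 respond (lower limit for 11/20: 31.5%). For one fixed definition, P(X ≥ 11) = 1.7%.
- For independent definitions, the chance that at least one does so is 1 − (1 − 0.0171)² = 3.4% for two and 1 − (1 − 0.0171)³ = 5.1% for three.
- Simulation (400,000 studies per setting, latent correlation 0, 0.5 or 0.8) gives the following for the best of two or three:

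| True rate | Mean reported rate | Lower-limit error, one fixed definition | Lower-limit error, best of 2–3 | Total coverage |
|---|---|---|---|---|
| 30% | 33.6–38.7% | 1.7% | 3.0–5.1% | 95–97% |
| 20–50% | 3.2–9.4 points too high | 1.0–2.1% | 1.8–6.0% | 94–98% |

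Total coverage barely moves because errors at the upper limit become rarer as errors at the lower limit become commoner.

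**Illustration 2: changing the percentage cut on the same diary data.** Let B and W be the headache-day counts at screening and week 4. Response at cut c means W ≤ (1 − c)·B with B > 0. If W ≤ 0.5·B then W ≤ 0.7·B, so every responder at 50% is also one at 30%. Loosening the cut can never lower the proportion, and a stricter cut can never raise it.

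For size, assume 7 days counted in each period. Each patient's daily headache probability is drawn from a beta distribution with mean m and intraclass correlation rho of 0.1–0.5. The week-4 probability is multiplied by 1 − (2/28)/m; for m = 0.6 this is 1 − 0.0714/0.6 = 0.881. Exact enumeration gives:

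| Mean m | 50% cut | 30% cut | 30% minus 50% | 75% cut |
|---|---|---|---|---|
| 0.5–0.8 | 6.7–25.2% | 12.8–37.3% | 5.5–13.3 points | 0.8–9.5% |
| 0.9–0.95 | 1.0–3.5% | 4.0–8.9% | 2.3–6.4 points | 0.05–1.3% |

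At rho = 0.3 the 50% and 30% cuts give 17.5% and 28.0% for m = 0.6, and 3.3% and 8.2% for m = 0.9. The first pair is about 4 and 6 of 20 patients, with exact intervals of 5.7–43.7% and 11.9–54.3%. Subtracting 2/28 from each patient's probability instead gives gaps of 5.0–12.8 points (m = 0.5–0.8) and 2.2–6.5 points (m = 0.9–0.95). An interval computed under its own fixed cut keeps about 96–99% coverage of that cut's rate. The problem here is a changed target, not a faulty interval.

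**The case against.** The strongest reply is that the plan already has a clear default. The clause sits in the diary section and never mentions the primary endpoint. The text that sets the primary endpoint gives one unconditional rule, and its back-reference most naturally points to that rule. Replacing it would mean departing from the analysis section. Protocol modifications go to the IRB with a new date and version number, and the primary and secondary endpoints "along with other required information for this study will be reported on ClinicalTrials.gov". The analysis is descriptive, with no test of the responder rate, and the continuous headache-day and headache-hour summaries are unaffected.

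Much of this stands. The 50% rule is the evident default, and the harm arises only if the permission is used to replace it. But naming a default does not revoke an express permission to depart from it. Registration and version control keep a record of changes without saying which reading holds, so a switch could be presented as following the protocol. A descriptive estimate is still biased if its definition is picked from the results.

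Two objections to the figures also stand. Illustration 1 fits only non-nested definitions; with percentage cuts the loosest always gives the highest proportion, and the shift is visible if the cut is stated. Illustration 2 uses the plan's 2-day difference, which is a difference to detect and not a predicted effect, and it does not match the plan's SD of 3. Scaled to 28 days, its SD of change is 3.5–7.1, and 6.4 for the 4-versus-6 example. The settings nearest to 3 (m = 0.95) show gaps of only 2.3–3.7 points. The gap need not vanish near that SD, however: counting over 28 days with m = 0.6 and rho = 0.3 gives SD 3.3, and 6.0% versus 17.2%. The conclusion rests on the wording, not on these figures.

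**Conclusion.** The concern holds and should be fixed. The plan expressly permits the response definition to follow the outcomes, and no section withdraws this or restricts it to supportive use. The consequence is conditional: a possible upward bias in the primary proportion, with interval errors shifted to the favourable side, and no effect on any formal test. Under the assumptions shown, the bias is about 3 to 9 percentage points for the best of two or three equal-rate, non-nested definitions. A move from a 50% to a 30% cut adds about 2 to 13 points in the 7-day diary model. That the clause is present and left open is certain; the size depends on alternatives and response rates that the plan does not state.

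**What to change.** Delete the sentence in the Daily Headache Diary section that allows other definitions according to outcomes. State in Statistical Methods & Analysis that a reduction of at least 50% in headache frequency from screening, assessed at the end of week 4 as Analysis Plans already has it, is the sole definition for the primary endpoint. List any other cuts of interest (for example 30% and 75%) as supportive before data are reviewed, and label anything added later as post hoc.

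The cost is protocol wording only; the sample size of 20 and its stated power do not change. What is lost is the freedom to redefine response after seeing results. This change does not settle the unit or the counting window of headache frequency, which needs its own clarification.

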By definition, HC responds to treatment with indomethacin, a nonsteroidal anti-inflammatory drug (NSAID) that has a structural similarity to serotonin and also inhibits nitric oxide-induced vasodilation^{4,5}. As with other indomethacin-responsive headache disorders, the mechanism by which it treats HC is not clear but there is some speculation that indomethacin may inhibit trigeminal nociceptive transmission and trigeminoautonomic activation^{6,7}. While patients with HC tend to respond within a matter of days to indomethacin, the literature reveals that most patients will relapse when it is discontinued and therefore will need to remain on it as a chronic treatment⁸. This can be problematic, as tolerability and risks of adverse effects with continued use remains a significant concern⁹. As an NSAID, the most common issue with indomethacin involves gastrointestinal complications, from indigestion and worsening acid reflux to gastric ulceration and hemorrhage. Patients may also experience renal insufficiency, and the drug can have an impact on blood pressure and platelet functioning among other things⁴. These risks are likely greater in patients with other co-morbid medical problems or on other

medications, or in the elderly who may have baseline renal and cardiac issues. There is a real need to find new treatment options for HC.

As there is significant overlap between HC and migraine, we anticipate that patients with HC will respond to treatment with erenumab.

Specific Aims:

1. Evaluate the response of hemicrania continua to treatment with erenumab
2. Evaluate the safety and tolerability of erenumab in patients with hemicrania continua

Methods:

Study Design: This is a prospective, open-label, study of patients with hemicrania continua treated with a single dose of erenumab 140 mg SQ.

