Participants: Up to 25 adult patients who are at least 18 years of age with hemicrania continua will be enrolled into the screening phase of this study at Mayo Clinic Arizona. Enrollment will stop once 25 subjects provide headache diary during the screening phase that meets eligibility criteria (i.e. meet diagnostic criteria for hemicrania continua). Exclusion and inclusion criteria will be modeled after those used in the phase 2 and 3 trials of erenumab for the prevention of migraine and adapted for the diagnosis of hemicrania continua.^{10,11} Potential participants will be excluded if they have active chronic pain conditions other than hemicrania continua (e.g. chronic pelvic pain) or acute pain conditions (e.g. recent surgery).

Subject Eligibility

Inclusion Criteria

- Adults ages 18 and over
- At least a 12 month history of hemicrania continua according to International Classification of Headache Disorders, 3rd Edition (ICHD-3)¹
- Previous or current complete response to indomethacin
- Stable preventive treatment for at least 2 months and no anticipated need to adjust/add current headache prevention treatment

Exclusion Criteria

- Nonresponse to a therapeutic dose of indomethacin for hemicrania continua when used for at least 1 week
- Pregnant or lactating subjects
- Use of barbiturate or opioid >6 days per month; history of chronic migraine
- History of previous trigeminal-autonomic cephalgia

- History within previous 2 months of interventional procedure for headache (occipital or other extracranial nerve block, sphenopalatine ganglion block, cervical facet block, facet rhizotomy)
- History of cranial nerve/rhizolysis
- Botulinumtoxin injection within previous 4 months
- Parenteral infusion of an oral corticosteroid use for more than 3 days within 4 weeks prior to screening phase

Screening Phase (1 week) (Day -7)

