At this initial visit, participants will be screened for inclusion/exclusion and data on their demographics, headache characteristics, current and past treatments, and medical history will be collected. Those meeting criteria for further participation will have measurement of vital signs and urine pregnancy testing (for women of childbearing potential), and will be trained on how to use the headache diary. Patients will be instructed to keep a prospective headache diary for the next week. We assume that up to 20% of individuals participating in the screening phase will not meet the inclusion criteria and/or diary compliance minimum and thus will not continue in this study. It is anticipated that 25 patients will be enrolled in the screening phase of the study to obtain 20 evaluable patients. If a subject is on indomethacin for the prevention of hemicrania continua, indomethacin will be stopped at this visit.

Baseline (treatment) Visit (Day 0)

Patients will return for a baseline visit after 1 week (i.e. 7 days since start of screening phase) of prospective headache diary collection. Diary compliance and eligibility for study inclusion will be assessed. Patients who still meet eligibility criteria will have measurement of vital signs and urine pregnancy testing will be conducted for women of childbearing potential. Levels of depression and anxiety will be measured using the Beck Depression Inventory and State-Trait Anxiety Inventory, respectively. Functional disability will be assessed with the Migraine Disability Assessment (MIDAS).

Treatment with Erenumab (Day 0)

Patients will receive treatment with 140 mg of erenumab via subcutaneous injection during their baseline visit. Patients will either be taught how to self-inject by a qualified research team member and then will do so under research team observation or receive the injections administered by a qualified research team member. Injections will be administered in the abdomen (except for a two inch area right around the navel), thigh, or outer area of upper arm (if someone else is injecting the patient) according to patient preference and will consist of two consecutive 70 mg injections. The second injection will not be given in the same spot as the first injection.

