An adverse event is defined as any untoward medical occurrence in a clinical trial patient. The event does not necessarily have a causal relationship with study treatment. The investigator is responsible for ensuring that any adverse events observed by the investigator or reported by the subject are recorded in the patient's record. The definition of adverse events includes worsening of a pre-existing medical condition. Worsening indicates that the pre-existing medical condition or underlying disease has increased in severity, frequency, and/or duration more than would be expected, and/or has an association with a significantly worse outcome than expected. A pre-existing condition that has not

worsened more than anticipated during the study or involves an intervention such as elective cosmetic surgery or a medical procedure while on study is not considered an adverse event.

Definition of Serious Adverse Events

A serious adverse event is defined as an adverse event that meets at least 1 of the following serious criteria:

- fatal
- life threatening (places the subject at immediate risk of death)
- requires in-patient hospitalization or prolongation of existing hospitalization
- results in persistent or significant disability/incapacity
- congenital anomaly/birth defect
- other medically important serious event

An adverse event would meet the criterion of “requires hospitalization,” if the event necessitated an admission to a health care facility (e.g., overnight stay). If an investigator considers an event to be clinically important, but it does not meet any of the serious criteria, the event could be classified as a serious adverse event under the criterion of “other medically important serious event.” Examples of such events could include allergic bronchospasm, hypersensitivity reaction, or events that necessitate an urgent intervention.

Reporting Procedures for Adverse Events That do not Meet Serious Criteria

The investigator is responsible for ensuring that all adverse events observed by the investigator or reported by the subject that occur after the dose of investigational product through the end of the safety follow-up visit (8 weeks after the last dose of investigational product) are reported using the Adverse Event case report form. The Adverse Event case report form is included within the Appendix of this protocol.

The investigator must assign the following adverse event attributes:

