- adverse event diagnosis or syndrome(s), if known (if not known, signs or symptoms)
- dates of onset and resolution (if resolved)
- intensity
- outcome
- action taken
- assessment of relatedness to investigational product

Assessment of whether the adverse event is possibly related to the investigational product is indicated by a “yes” or “no” response to the question: “Is there a reasonable possibility that the event may have been caused by the investigational product?”

The member of the research team who receives the information from the participant about the adverse event will complete the Adverse Event case report form. The Principal Investigator will always be responsible for initially and dating the form, indicating that the Principal Investigator has reviewed the adverse event with the research team member, determining the relationship of the adverse event to the study, and determining if the adverse event meets criteria for a serious adverse event.

Reporting Procedures for Serious Adverse Events

The investigator is responsible for ensuring that all serious adverse events observed by the investigator or reported by the subject that occur after signing of the informed consent through the end of the safety follow-up visit (8 weeks after the last dose of investigational product) are recorded in the subject’s record and to the local Institutional Review Board according to that Board’s policy.

Reporting of adverse events to Amgen will occur in accordance with the “Safety Data Exchange Requirements” as provided by Amgen. These requirements dictate the need for and timing of reporting adverse events to Amgen. A copy of the “Safety Data Exchange Requirements” has been included within the Appendix of this protocol. Please see Appendix 1.

Annual reporting requirements:

Adverse events, any protocol non-compliance and UPIRTSOs will be reported to the reviewing Institution Review Board (Mayo Clinic IRB) at the time of annual IRB continuing review, in accordance with Mayo Clinic research policies.

Subject Risks and Benefits

Possible Benefits:

As this is an open-label study, all participants will receive treatment with erenumab. It is likely that many patients will have improvements in their headache patterns following treatment with erenumab, as has been demonstrated in the phase II and III clinical trials and by the US Food and Drug Administration approval.

Possible Risks:

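### Non-serious adverse events have no scheduled enquiry, form entry or analysis between the indomethacin stop (Day -7) and the erenumab dose (Day 0)

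*Combined protocol and SAP*

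**What the plan says.** All references are to the combined protocol and SAP.

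- **Screening Phase (Day -7):** "If a subject is on indomethacin for the prevention of hemicrania continua, indomethacin will be stopped at this visit". This does not apply to everyone, since the Inclusion Criteria admit subjects with "Previous or current complete response to indomethacin". The background says of indomethacin that "most patients will relapse when it is discontinued".
- **Adverse Events (definition):** "An adverse event is defined as any untoward medical occurrence in a clinical trial patient". No causal link to treatment is needed. Also, "The definition of adverse events includes worsening of a pre-existing medical condition", but only where the worsening exceeds what would be expected.
- **Adverse Events (general duty):** the investigator must see that "any adverse events observed by the investigator or reported by the subject are recorded in the patient's record". No start time is given.
- **Reporting of non-serious events:** the Adverse Event form is used for events "that occur after the dose of investigational product through the end of the safety follow-up visit".
- **Reporting of serious events:** these are collected if they are events "that occur after signing of the informed consent through the end of the safety follow-up visit".
- **Schedule of Events:** the adverse event row is marked for weeks 1-4, Day 28 and Day 56. It is blank for the screening phase and the baseline visit.
- **Adverse Events Analysis:** the safety set is subjects who received erenumab. The text promises to report the relationship of events to the study as well as to the study treatment.

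**The concern.** A window for non-serious events that opens at the dose is natural when nothing is done to the subject beforehand. Here something is: for subjects still on indomethacin, the protocol itself withdraws a treatment at Day -7. The plan treats this week as safety-relevant for serious events but not for non-serious ones.

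Two things are at stake. First, non-serious harm from a study-directed change does not reach the adverse event dataset, and a subject who stops indomethacin but is never dosed falls outside the safety set altogether. Second, Specific Aim 2 is safety and tolerability, and there is no control arm. The subject's own pre-dose state is then the main comparison for judging whether an early post-dose event is due to erenumab. The two drugs also overlap in the systems they affect. The background names gastrointestinal and blood pressure effects of indomethacin. Possible Risks names constipation and hypertension for erenumab, with hypertension reported most often within seven days of dosing. A change in either system around Day 0 is hard to attribute without knowing what was present before the injection.

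**Working it through.** **1. The plan's own screening figures.** The Screening Phase section gives 25 screened, up to 20% lost and 20 evaluable. 20 / (1 - 0.20) = 25, so the figures agree. Hence up to 25 - 20 = 5 screened subjects may never be dosed. Any of these who were on indomethacin would have stopped it.

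**2. Length of the gap.** From Day -7 to Day 56 is 7 + 56 = 63 days, of which 7 precede the dose: 7/63 = 11.1%. The screening visit has a window of -2 days. If it is used in full, with Day 56 kept nominal, the figure is 9/65 = 13.8%.

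**3. What reaches Day -7 to Day 0.**

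| Source | Start | Covers the withdrawal week? |
|---|---|---|
| Serious event reporting | Consent | Yes |
| Duty to note events in the patient's record | Not stated | Yes, if observed or volunteered |
| Adverse Event form, non-serious | After the dose | No |
| Scheduled enquiry | Weeks 1-4 column | No |
| Safety analysis | Dosed subjects | No pre-dose table |

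The weekly column is labelled from Day 0, but the form rule opens only after the dose, so that column does not reach back. Table layout can suffer in text extraction, but the blank cells agree with the form rule.

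**4. What pre-dose reference exists.** The daily diary covers headache. Vital signs are taken at Day -7 and Day 0. The depression, anxiety and disability questionnaires are completed at Day 0. Medical history, headache characteristics and concomitant medications are scheduled at Day -7 but not at Day 0, so they describe the state before withdrawal. Gastrointestinal and other non-headache symptoms in that week have no systematic source.

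**5. Weight of one event.** With 20 dosed subjects, one subject moves a proportion by 1/20 = 5 percentage points. Possible Risks quotes about 3% for constipation, which is 0.03 × 20 = 0.6 subjects. A single wrong attribution would therefore exceed the number expected at that rate.

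**6. How many subjects are affected.** The number who stop indomethacin is 25 × s, where s is the share taking it at screening. The documents do not give s, so the number lies anywhere from 0 to 25. The number with a non-serious event also needs a withdrawal-week event rate, which is not given either.

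**7. Sample size.** The stated 80% power reproduces. With n = 20, a decrease of 2 days and SD 3 (read as the SD of the change), the noncentrality is (2/3) × √20 = 2.98 on 19 degrees of freedom, and two-sided power at 0.05 is 80.7%. Collecting adverse events earlier changes none of this.

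**The case against.** The strongest reply is that the post-dose window fits its purpose. Aim 2 concerns erenumab, and the safety set is dosed subjects. Much of the withdrawal week is also covered by other means, and each of the following tempting inferences goes too far.

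- **That harms of this week go unrecorded.** The Adverse Events section requires any observed or reported event to be noted in the patient's record, with no start date. Serious events are captured from consent, the investigator may class a clinically important event as serious, and the annual report to the IRB has no post-dose limit. What is missing is active enquiry, form entry and analysis.
- **That no pre-dose reference exists.** The diary and the two sets of vital signs provide one for headache and vital signs.
- **That every relapse off indomethacin is a missed adverse event.** Worsening counts only beyond what would be expected, and the background makes relapse expected. Ordinary relapse may not qualify in any window. Excess worsening and other symptoms would.
- **That withdrawal events contaminate the erenumab proportions.** The form rule excludes events with pre-dose onset, and onset date is a required attribute. Contamination is therefore possible but not shown.

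These replies narrow the point without removing it. A note in the patient's record does not feed the planned tables. An onset date collected only after dosing depends on recall: if the first weekly enquiry falls at Day 7, a symptom that began on Day -7 is dated 14 days later. A condition that starts before Day 0 and persists or worsens afterwards remains ambiguous.

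**Conclusion.** The point holds as a gap in systematic capture of non-serious events, and correcting it is a cheap improvement. It does not touch the primary endpoint, the sample size or any clinical rule, and it takes no view on whether indomethacin should be stopped. The gap is 11.1% of the observation period (up to 13.8% with the visit window), and up to 5 screened subjects could lie outside the safety set. Its effect is to weaken attribution of early post-dose events other than headache and vital signs.

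A reader might go on to give a count of affected subjects. For example, 25-75% of 20 would be 5-15. The documents do not support this: the share is an assumption, and it counts subjects who stop indomethacin, not subjects with a missed or misattributed event. The 5-point figure is only the weight of one subject in 20, not an estimate of bias.

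**What to change.** 1. In the reporting procedures for non-serious adverse events, start form collection at consent, as already done for serious events. This also reconciles the open-ended duty to note events in the patient's record with the two different reporting windows.
2. In the Schedule of Events, mark adverse events at the Day 0 visit, with the enquiry made before the injection.
3. In the Adverse Events Analysis, tabulate events with pre-dose onset separately from post-dose events, and include screened subjects who are never dosed. Keep the erenumab event proportions based on post-dose onset or post-dose worsening in dosed subjects.

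The visit and the form already exist. The cost is slightly more form completion and one extra table.
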